9.1 Power and Sample Size Determination

Assuming an effect size of 0.80 of the primary efficacy endpoint (PERMP-T score averaged over all post-dose time points assessed at Visit 5) between AMPH ER Tabs and placebo and approximately 92 completers, this study will have at least 93% power at the level of 0.05 (2-sided). To allow for an estimated 15% potential dropout rate, this study plans to enroll approximately 108 subjects to ensure that at least 92 complete. The study will be conducted in approximately 6 cohorts of 18 subjects because subjects will need to be enrolled in cohorts to facilitate the administration of serial PERMPs at Visits 5. An additional cohort of up to 18 subjects may be added to ensure at least 92 subjects complete the study if there are circumstances in which any of the cohorts are unable to enroll 18 subjects, or if the dropout rate is higher than expected (>15%) thereby having less than 92 completers to ensure sufficient statistical power.

The assumed effect size of 0.80 (expected treatment difference of 18 in average PERMP-T score divided by between-subject square root mean square error of 21.75) is based on differences measured between active and placebo in previous laboratory school studies conducted with similar drug formulations.

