Indication	ADHD (Attention-deficit/hyperactivity disorder)
Sample Size	Approximately 108 subjects – Maximum allowable cohort size of 18 subjects at up to 3 sites
Treatment Duration	~11 weeks
Main Entry Criteria	Adult male and female subjects aged 18 to 60 years who meet Diagnostic and Statistical Manual of Mental Disorders, Fifth Edition (DSM-5) criteria for ADHD, otherwise healthy.
Test Product	Amphetamine Extended-Release Tablets (AMPH ER TAB), 5, 10, 15 or 20 mg (manufactured by Tris Pharma, Inc., USA)
Reference	Matching placebo including flavor, 5, 10, 15 or 20 mg (manufactured by Tris Pharma, Inc., USA)
Objectives	Efficacy Objective: To evaluate the efficacy of AMPH ER TAB compared to placebo in adult patients with ADHD aged 18–60 years.
	Safety Objective: To assess the safety and tolerability of AMPH ER TAB in adult patients with ADHD aged 18–60 years.
Methodology	This is a randomized, double-blind (DB), placebo-controlled, parallel, study to assess the efficacy and safety of AMPH ER TAB compared to placebo for the treatment of ADHD in adults aged 18 to 60 years.
	After Screening and Baseline evaluations are complete, eligible subjects will be randomized in the study to take DB AMPH ER TAB or matching placebo orally once daily in the morning beginning the day after the Baseline visit.
	There will be a 5-week DB dose titration phase. The starting dose of AMPH ER TAB or matching placebo will be 5 mg in the morning before 10 am, with or without food, swallowed whole or chewed. Subjects will then be titrated up by 5 mg increments each week. After Visit 3 subjects will receive a final dose of 20 mg for 14 (± 3) days prior to Visit 5. Subjects who cannot tolerate the study drug will be discontinued from the study.
	A Permanent Product Measure of Performance (PERMP) placement test will be done at Screening or at Baseline. PERMP practice sessions will be done before and after efficacy and safety assessments during Baseline and Visits 1 to 3. An abbreviated administration of serial PERMPs will take place at Visit 4 where PERMP will be administered at pre-dose, 0.5, 1, 2 and 4 hours post-dose.
	At Visit 5, efficacy assessments will include the administration of serial PERMPs at pre-dose and at 0.5, 1, 2, 4, 8, 10, 12, 13, and 14 hours post-dose.

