7 RANDOMIZATION AND BLINDING PROCEDURES

Enrollment will occur after all Screening procedures have been performed and eligibility for the study is confirmed at Baseline. After Baseline, subjects will enter a 4-week randomized, DB, placebo-controlled phase. Subjects will be randomized at Baseline to take DB AMPH ER TAB (or matching placebo) orally once daily.

All study drug product samples will be supplied in identical containers and will be similar in physical characteristics (color, smell, flavor, and appearance), thereby enabling DB conditions.

Unblinding should occur only when knowing the treatment assignment has a bearing on the medical treatment or evaluation of a subject. Whenever possible, the need to unblind should be discussed with the Sponsor prior to unblinding. For emergency unblinding, study personnel will use the IWRS unblinding module.

Table 6 Sponsor's Contact Information for Unblinding Procedures

Contact	Phone number	Fax number
Tris Pharma, Inc		
[name] Director, Regulatory Affairs	Direct # [contact]	NA
[contact]		

A subsequent written report, including all pertinent details, must be submitted to the Sponsor within 24 hours of the unblinding. Whenever possible, the blind of the subject should be maintained.

If Investigator or site personnel or subject unblinded, the subject must be withdrawn from the study, and procedures accompanying withdrawal are to be performed.

Confidential Page 40 of 67

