9.3.5 Efficacy Analyses

9.3.5.1 Primary Efficacy Analysis

The primary efficacy endpoint and estimand are defined in Section 3.2.1.

PERMP-T scores at all post-dose time points (0.5, 1, 2, 4, 8, 10, 12, 13, and 14 hours post-dose) at visit 5 will be assessed using a linear MMRM analysis. This is a restricted maximum likelihood (REML)-based analysis implemented using SAS PROC MIXED. The model will include treatment, time and treatment by time as fixed effects and subject as a random effect. Pre-dose PERMP-T score will be included as a covariate. The difference between AMPH ER TAB and placebo will be assessed at the alpha = 0.05 level of significance. The covariance structure used in the final MMRM model will be the one that has the lowest Akaike Information Criterion (AIC) among the following selections: SP(POW), unstructured, compound symmetry (CS), heterogeneous CS or heterogeneous Toeplitz. Kenwood-Roger correction will be used to estimate denominator degrees of freedom. The treatment effect is estimated by the overall adjusted least square mean difference between two treatment groups. 95% CI for the adjusted least square mean will be constructed and p-value for the treatment comparison will also be provided.

The primary efficacy analysis will be conducted on the mITT population.

For the primary efficacy analysis, the MMRM model will be fit to the observed data with missing at random assumption. The rate of missing PERMP-T for at least one post-dose time point on will be calculated and summary (number and percentage) of subjects discontinued prior to Visit 5 by the

Confidential Page 50 of 67

dose level (5, 10, 15, 20 mg) prior to discontinuation will be summarized. Sensitivity analysis will be performed using Multiple Imputation approach with missing not at random assumption. In this analysis, the mean difference between the (unobserved) missing values and observed values (refer to as shift) will be assumed to vary independently for the different treatment groups. More details of this procedure will be provided in SAP.

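### Neither site nor cohort is stated as a randomisation stratum or appears in the primary MMRM, which may cost some precision; stratify on one low-dimensional factor and put that factor in the model

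*Combined protocol and SAP*

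**What the plan says.** Section 9.1 of the protocol states that "The study will be conducted in approximately 6 cohorts of 18 subjects because subjects will need to be enrolled in cohorts" so that the serial PERMPs can be run, and allows one further cohort of up to 18. The sample-size row of the Synopsis adds "Maximum allowable cohort size of 18 subjects at up to 3 sites". That wording does not settle whether a cohort belongs to one site or spans several.

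On randomisation, section 7 says only that "Subjects will be randomized at Baseline to take DB AMPH ER TAB (or matching placebo) orally once daily". It gives no allocation ratio, block or stratification factor.

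On the model, section 9.3.5.1 says "The model will include treatment, time and treatment by time as fixed effects and subject as a random effect", with the pre-dose PERMP-T score as covariate. The Synopsis and section 3.2.1 describe the same terms. Section 4.2.10.5 places the pre-dose test at Visit 5, in the same series as the nine post-dose tests. Section 9.3.5.2 applies the same model to the key secondary time points.

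Section 9 defers detail to an SAP to be finalised before unblinding. Section 9.2 says departures from the protocol's statistical plan must be reported and justified.

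**The concern.** Site and cohort are known before randomisation and are created by the design itself. Scores may differ between them. If they do, and the model ignores the grouping, the variation between groups is counted as subject-level noise. Two consequences are possible:

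- If arms are balanced within cohort, the treatment estimate is free of cohort differences but its standard error still includes them. The interval is then too wide and the test conservative.
- If arms are not balanced within cohort, chance imbalance adds real noise to the treatment difference. The standard error reflects it correctly, but some of it could have been avoided.

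Any loss would fall on the primary comparison and on the nine gated time-point tests in section 9.3.7.1, where one failure stops all later claims. The plan gives no reason for leaving both factors out.

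**Working it through.** **Inputs from section 9.1.** "Assuming an effect size of 0.80 of the primary efficacy endpoint"; "expected treatment difference of 18 in average PERMP-T score divided by between-subject square root mean square error of 21.75"; "approximately 92 completers"; two-sided 0.05; about 6 cohorts.

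**Assumptions.** Allocation is 1:1, so 46 per arm, because no ratio is stated. ρ is the share of residual variance, after the pre-dose covariate, that is due to cohort. It is not in the documents and is varied.

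**The plan's own figure.** Power is approximately Φ(d√(46/2) − 1.96).

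- d = 0.80: 0.80 × 4.796 = 3.837, power 97.0% (96.7% by noncentral t).
- d = 18/21.75 = 0.828: power 97.8% (97.5% by noncentral t).

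The plan's claim of at least 93% is therefore true as a lower bound, although 93% itself is not what these inputs give. (The quotient is 0.83 rather than the stated 0.80; that is a separate matter.)

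**Interval without cohort.** SE = 21.75 × √(2/46) = 4.535. With 92 − 3 = 89 df, t = 1.987 and the half-width is 9.01 points.

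**Interval with five cohort terms.** df = 84 and t = 1.989.

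- Balanced within cohort: half-width = 1.989 × 4.535 × √(1 − ρ).
- Unstratified: the same divided by √(1 − 5/91), for chance imbalance of arms across cohorts.
- Type I error if arms are balanced within cohort but cohort is ignored: 2·P(T₈₉ > 1.987/√(1 − ρ)).

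| ρ (assumed) | Stratified: half-width, change | Unstratified: half-width, change | Type I error, stratified, cohort ignored |
|---|---|---|---|
| 0 | 9.02, +0.1% | 9.28, +3.0% | 5.0% |
| 5% | 8.79, −2.5% | 9.04, +0.3% | 4.4% |
| 10% | 8.56, −5.1% | 8.80, −2.3% | 3.9% |
| 20% | 8.07, −10.5% | 8.30, −7.9% | 2.9% |

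Without stratification the term pays only above ρ of about 5/91 = 5.5%.

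**Number of levels.**

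- Site only, 3 levels, unstratified, no site effect: 1/√(1 − 2/91) = 1.011, about 1% wider.
- Site by cohort, up to 3 × 6 = 18 cells of about 92/18 = 5 completers, unstratified: 1/√(1 − 17/91) = 1.109, about 11% on the SE unless ρ exceeds about 0.19.

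**What the covariate absorbs.** This was simulated with 2,000 runs per setting, using ANCOVA on the averaged post-dose score as a stand-in for the MMRM. Pre/post correlation ran from 0.6 to 0.9 and cohort share of the raw score from 5 to 20%. The ratio of half-widths, without cohort to with cohort, was:

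- Cohort shift identical before and after dosing: 1.00–1.02 stratified, 0.97–0.99 unstratified.
- Shifts correlated 0.5: about 1.00–1.39.
- Shifts unrelated: about 1.01–1.65.

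With cohort left out, type I error stayed near 5% under unstratified randomisation and fell below 5% under stratified randomisation.

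**Power if 21.75 excludes cohort variation.** The SD becomes 21.75/√(1 − ρ). Power without a cohort term is 96.9, 96.1, 94.0 and 90.7% at ρ = 5, 10, 20 and 30%. The most extreme simulated setting (correlation 0.9, unrelated shifts, raw share 20%, unstratified) gave 67% without cohort and 97% with it. The half-width ratio there was 1.59, which implies a residual share of about 1 − 1/1.59² = 60%.

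**The case against.** A reader might infer that all site and test-day variation stays in the error term and must widen the interval. The documents do not support that. The pre-dose covariate is taken in the same Visit 5 session, so a shift common to pre- and post-dose scores is largely gone before cohort is considered. In that case an unstratified cohort term makes the interval slightly wider. This objection stands, and it limits the point to variation that differs between pre-dose and post-dose testing.

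A reader might also infer a validity problem. There is none: the omission causes no bias, and type I error is at or below its nominal level.

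Two further inferences lack support. The protocol does not say that cohort members share a room, staff or even a test day, and visits carry a ±3-day window. It gives no expected effect by time point, so nothing shows that early or late times have the least margin; the gating order is not a margin.

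It is also fair to say that covariate choice is discretionary when validity is unaffected, that stated assumptions leave power above the promised 93%, and that stratification may be set out in the IWRS specification or the SAP. Against this, section 9.3.5.1 already fixes the model terms, so the protocol is where the choice should be recorded and explained.

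**Conclusion.** The point holds as a minor, inexpensive improvement in precision. The grouping exists, no stratification is stated, and neither factor is in the model. What is lost depends on a residual share that the documents do not give. With arms balanced within cohort, the term costs about 0.1% in interval width when there is no cohort effect and saves 2.5% at a 5% share and 5.1% at 10%. The last saving is equivalent to about 10 more completers (92/0.90 = 102). Without balance the gain is smaller and becomes a loss below a share of about 5.5%. The stratum and the model term therefore belong together. Power stays above 90% for residual shares up to 30%, even if 21.75 excludes cohort variation. These figures assume 1:1 allocation, 92 completers, 6 equal cohorts and a single averaged score in place of the full MMRM.

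**What to change.** 1. In the protocol, define how cohorts relate to sites.
2. In section 7, have the IWRS randomise in blocks within one low-dimensional factor: cohort if each cohort sits at one site, otherwise site.
3. In section 9.3.5.1, add that same factor as a fixed main effect for the primary and key secondary tests, with a rule for pooling sparse levels set before unblinding. Carry the term into section 3.2.1 and the Synopsis.
4. Do not fit a full site-by-cohort factor of up to 18 cells.
5. If subjects have already been randomised without stratification, add site only and pre-specify cohort as a sensitivity analysis.

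The cost is an IWRS setting, one model term and 2 to 5 degrees of freedom. In the site-only fallback, the interval is about 1% wider if sites do not differ.

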9.2 Analysis Populations

The analysis populations are defined as follows:

- **Safety Population (SAF)**: The safety population is defined as all enrolled subjects who received at least one dose of study drug, with treatment assignment based on the actual treatment received.
- Randomized Population (RAND): The randomized population is defined as all randomized subjects, with treatment assignment based on the randomized treatment (regardless of actual treatment received).
- Intent-To-Treat Population (ITT): The ITT population is defined as all randomized subjects who received at least one dose of study drug treatment, with treatment assignment based on the randomized treatment (regardless of actual treatment received).
- **Modified Intent-To-Treat Population (mITT)**: The mITT population is defined as all subjects who are in the ITT population and have at least one PERMP-T score at Visit 5.

The primary efficacy analysis and key secondary efficacy analysis will be performed on the mITT population. Analysis of additional secondary endpoints will be performed for ITT population.

Confidential Page 49 of 67

The safety analyses will be performed on the safety populations.

Deviations from the original statistical plan as planned in this protocol will be reported and justified in the SAP and clinical study report (CSR) as appropriate.

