- 21. Answer of "yes" to questions 4 or 5 of the C-SSRS within the last 2 years.

Confidential Page 7 of 67

Assessments

- CGI-S
- AISRS DSM-V Update
- DSST
- ACDS DSM-V Update
- M.I.N.I. 7.0.2
- PERMP
- C-SSRS
- Questionnaire for Sleep, Appetite, Mood and Psychotic Adverse Events
- Adverse Events
- Electrocardiogram
- Safety Labs
- Physical Exam
- Vital Signs
- · Body weight
- Medical History
- Concomitant Medications

Statistical Analysis

Efficacy:

The primary efficacy estimand is defined by the following 3 components:

- a. Target population: adult patients with ADHD aged 18 to 60 years who can tolerate AMPH ER TAB at 20 mg once daily.
- b. Primary efficacy endpoint: PERMP-T score over all post-dose time points assessed during the administration of serial PERMPs at Visit 5
- c. Measure of intervention effect: treatment difference in means averaged over all postdose time points for endpoint described above between AMPH ER TAB and placebo in target population regardless of use of any concomitant medications.

The primary efficacy endpoint will be assessed using a linear Mixed Model Repeated Measures (MMRM) analysis. This is a restricted maximum likelihood (REML)-based analysis implemented using SAS^{\circledast} PROC MIXED. The model will include treatment, time and treatment by time as fixed effects and subject as a random effect. Pre-dose PERMP-T score will be included as a covariate. The difference between AMPH ER TAB and placebo will be assessed at the alpha = 0.05 level of significance. The covariance structure used in the final MMRM model will be the one that has the lowest Akaike Information Criterion (AIC) among the following selections: SP(POW), unstructured, compound symmetry (CS), heterogeneous CS or heterogeneous Toeplitz. Kenwood-Roger correction will be used to estimate denominator degrees of freedom. The treatment effect is estimated by the overall adjusted least square mean difference between two treatment groups. 95% CI for the adjusted

Confidential Page 8 of 67

least square mean will be constructed and p-value for the treatment comparison will also be provided.

Key secondary efficacy outcomes as determined by the comparison of each PERMP-T score at each time point (0.5, 1, 2, 4, 8, 10, 12, 13, and 14 hours post-dose) with pre-dose PERMP-T scores at Visit 5 are:

- Onset of clinical effect
- Duration of clinical effect

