3 STUDY DESIGN

3.1 Design

Figure 1: Study Design

This is a randomized, double-blind (DB), placebo-controlled, parallel, study to assess the efficacy and safety of AMPH ER TAB compared to placebo for the treatment of ADHD in adults aged 18 to 60 years.

After Screening and Baseline evaluations are complete, eligible subjects will be randomized to take double-blinded (DB) AMPH ER TAB or matching placebo orally once daily in the morning beginning the day after the Baseline visit.

There will be a 5-week DB dose titration phase. The starting dose of AMPH ER TAB or matching placebo will be 5 mg in the morning before 10 am, with or without food, swallowed whole or chewed. Subjects will then be titrated up by 5 mg increments each week. After Visit 3 subjects will receive a final dose of 20 mg for 14 (± 3) days prior to Visit 5. Subjects who cannot tolerate the study drug will be discontinued from the study.

A Permanent Product Measure of Performance (PERMP) placement test will be done at Screening or Baseline. PERMP practice sessions will be done before and after efficacy and safety assessments during

Confidential Page 21 of 67

Baseline and Visits 1 to 3. An abbreviated administration of serial PERMPs will take place at Visit 4 where PERMP will be administered at pre-dose, 0.5, 1, 2 and 4 hours post-dose.

At Visit 5, efficacy assessments will include the administration of serial PERMPs at pre-dose and at 0.5, 1, 2, 4, 8, 10, 12, 13, and 14 hours post-dose.

AISRS and CGI-S will be conducted at Baseline and Visits 1 to 5. DSST will be administered at Baseline and Visit 5.

Safety assessments will include treatment-emergent adverse events, physical examination, vital signs, body weight, Columbia Suicide Severity Rating Scale (C-SSRS), and direct questioning to assess for sleep, appetite, mood and psychotic adverse events.

A schematic of the overall study design is presented in Figure 1.

The full schedule of events is found in Appendix A.

This study will be conducted in the United States.

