4.2.10.6 Early Termination Visit

The following activities may be done for subjects that withdraw prior to completion of Study Visit 5 (i.e., terminate early):

- Physical examination
- Body weight

Confidential Page 34 of 67

- BP and pulse (average of triplicate measurements)
- AE assessment
- Concomitant medications assessment
- "Since Last Visit" C-SSRS
- Questionnaire for Sleep, Appetite, Mood, and Psychotic Adverse Events
- AISRS
- CGI-S
- DSST
- Study drug accountability and reconciliation
- A urine pregnancy test (for females of child-bearing potential only) may be performed in the event of a suspected pregnancy per Investigator's clinical judgment
- Any other assessments as determined by the Investigator

For all activities performed, the results are to be recorded in the eCRF.

Confidential Page 35 of 67

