9.3.7.2 Missing Data

No imputation of missing PERMP scores will be done for the primary efficacy analysis. To evaluate the sensitivity of the primary analysis results to the use or non-use of imputation, analyses using multiple imputation methods will be conducted as mentioned in Section 9.3.5.1. Additional details will be described in the SAP.

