APPENDIX C. REVISION HISTORY

Version 1.0 to Version 2.0

A major update on the study design was applied to this protocol to reflect feedback from the FDA:

"The study should be randomized and double-blind with parallel groups (i.e., not cross-over). Patients should be randomized to treatment or placebo from baseline (i.e., no open-label, "dose optimization" period should be included). Treatment arms should include fixed doses; a short, double-blind dose-titration period is acceptable. You should measure pulse, blood pressure, and weight at every clinic visit. You should use direct questioning to assess for sleep, appetite, mood, and psychotic adverse events rather than relying on spontaneous reports.

The PERMP is an acceptable outcome measure; however, you should describe the simulated work environment/testing day in the submitted protocol. Additionally, you should use the CGI-Severity at multiple time points to assess improvement rather than the CGI-I (which is prone to recall bias). From a statistical perspective, we recommend that you pre-specify the estimand and provide the rationale for your choice. You should justify that the proposed primary efficacy analysis is suitable for the chosen estimand, and pre-specify sensitivity analyses for your missing data assumptions."

DSST was included as a secondary efficacy assessment.

Version 2.0 to Version 3.0

Update to the statistical sections was applied to this protocol to reflect feedback from the FDA:

Efficacy endpoints have been updated.

ANCOVA was replaced by MMRM for primary and key secondary endpoints analyses.

Sensitivity analysis has been updated to use MI method based on missing not at random assumptions to assess impact of potential imbalances in dropouts before visit 5. Summary of PERMP-T practice scores to be provided by completers/dropouts category to check potential trends.

Sample size justification has been updated.

Primary analysis population has been updated to be a modified ITT (mITT) population which will include the subjects who have at least one PERMP-T score at Visit 5. The primary efficacy analysis and key secondary analysis will be conducted on the mITT population.

Definition of mITT population has been added.

Confidential Page 66 of 67

Included details on in which circumstances an additional cohort of 18 subjects will be added.

Alcohol restriction has been added (from Baseline to 24 hours after Visit 5).

Version 3.0 to Version 3.1

Exclusion criteria #6 updated to:

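### Does the mITT set miss the 20 mg tolerators that the primary estimand names, and is the set for the planned imputation left open?

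*Combined protocol and SAP*

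**What the plan says.** The synopsis and Section 3.2.1 define the population of the primary estimand in the same words: "Target population: adult patients with ADHD aged 18 to 60 years who can tolerate AMPH ER TAB at 20 mg once daily". The treatment effect is the difference in mean PERMP-T between the arms within that population.

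Section 9.2 defines the primary analysis set by attendance: "The mITT population is defined as all subjects who are in the ITT population and have at least one PERMP-T score at Visit 5". Section 3.1 states "Subjects who cannot tolerate the study drug will be discontinued from the study", and Section 4.2.10.3 repeats it for the titration visits. Section 4.2.10.6 introduces the early termination assessments with "The following activities may be done for subjects that withdraw prior to completion of Study Visit 5", and PERMP is not among those listed. Section 3.6 encourages withdrawing subjects to complete the final visit, so a few leavers may still provide a Visit 5 score.

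Section 9.3.5.1 fits the MMRM to Visit 5 scores under missing at random. On the covariate it says "Pre-dose PERMP-T score will be included as a covariate". It then adds "Sensitivity analysis will be performed using Multiple Imputation approach with missing not at random assumption", with shifts that vary independently by arm, and leaves the details to the SAP. Section 9.3.7.2 gives the aim as "To evaluate the sensitivity of the primary analysis results to the use or non-use of imputation" and refers back to 9.3.5.1. Neither section names the analysis set for the imputation. Appendix C gives the reason for introducing it: "to assess impact of potential imbalances in dropouts before visit 5".

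**The concern.** The two arms of the mITT are filtered differently. An active subject has to stay on active drug to be counted, whereas a placebo subject only has to stay on placebo. Subjects who would have failed on active drug therefore remain in the placebo mean and are gone from the active mean. If they perform differently on placebo, the estimate is off for the population it claims to describe, in a direction nobody can know.

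Missing at random does not cover this. The model uses Visit 5 data only, so the assumption concerns time points missed within that day. The pre-dose covariate is also measured at Visit 5, after about five weeks of randomised treatment, so adjusting for it cannot be presumed to restore the balance.

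The imputation raises a second doubt. Subjects lost before Visit 5 are outside the mITT by definition. If the imputation were run on the mITT, it would reach none of them and could not serve its stated purpose.

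**Working it through.** **The plan's own figures (Section 9.1).** The plan gives about 108 enrolled, 15% dropout, 92 completers, effect size 0.80 and power of at least 93%.
- Completers: 108 × 0.85 = 91.8. Dropouts: 108 × 0.15 = 16.2, so about 16.
- Power with 46 per arm (1:1 assumed, since the ratio is not stated): 0.80 × √(46/2) = 3.84, and 3.84 − 1.96 = 1.88, which gives 97%. The plan's figure holds as a lower bound.
- The quoted inputs give 18/21.75 = 0.83, slightly above 0.80.

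**Bias against the tolerator target.** Divide subjects by what they would do on each arm: a share *c* leaves on either arm, *a* only on active, *b* only on placebo, and *s* = 1 − a − b − c on neither. Take any departure on active as non-tolerance. The active mITT is then s + b, which is the target group, and the placebo mITT is s + a. With gA and gB the residual SDs by which the *a* and *b* groups score below *s* on placebo:

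bias = 21.75 × [a/(s+a) × gA − b/(s+b) × gB]

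The dropout split, the overlap and the shifts below are assumptions; the documents give none of them.

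| Dropout active/placebo | Overlap c | Who scores lower | Bias at 0.5 SD | Bias at 1 SD |
|---|---|---|---|---|
| 20%/10% | 10% | active-only leavers | +1.2 | +2.4 |
| 20%/10% | 5% | active-only leavers | +1.8 | +3.6 |
| 20%/10% | 5% | both kinds | +1.1 | +2.3 |
| 20%/10% | 5% | placebo-only leavers | −0.7 | −1.4 |
| 15%/15% | 15% | any | 0 | 0 |
| 15%/15% | 7.5% | active-only leavers | +1.0 | +1.9 |
| 15%/15% | 7.5% | placebo-only leavers | −1.0 | −1.9 |
| 15%/15% | 7.5% | both kinds equally | 0 | 0 |

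First row as an example: a = 0.10, b = 0, s = 0.80, a/(s+a) = 0.111, and 0.111 × 21.75 × 0.5 = 1.2. A shift of 0.25 SD in that row would give 0.6.

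The extreme case puts all 16 dropouts on active and none on placebo, with a 1 SD shift: 16/54 × 21.75 = 6.4 points.

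**Size relative to the design.** At 20%/10% with 54 randomised per arm, 43.2 and 48.6 subjects remain, so SE = 21.75 × √(1/43.2 + 1/48.6) = 4.55. If 3.6 of an observed 18 points were spurious, the rest would still be (18 − 3.6)/4.55 = 3.2 SE. With no effect among tolerators, the bias would matter more. Suppose 15% of the placebo mITT are would-be non-tolerators with a shift of 0.25 to 1 SD: the bias is 0.8 to 3.3 points and two-sided rejection is 5.4% to 11.1%.

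**What the imputation can do.** On the mITT it would cover 0 of about 16 early leavers. On the ITT set it would cover all who were dosed. If missing active subjects are given the placebo mean, the difference falls from 18 to 18 × (1 − 8/54) = 15.3 with 8 lost per arm, 14.0 with 12 lost on active and 4 on placebo, and 12.7 with all 16 on active. A simulation at 20%/10% dropout (assumed pre-dose SD 60, slope 0.8, practice-to-pre-dose correlation 0.8) gave (18 − 0.20 × 38)/5.05 = 2.06 and (18 − 0.20 × 40)/5.12 = 1.95. Against a critical value of about 1.99, active dropouts would need to score about 39 points (1.8 SD) worse before significance was lost.

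**The case for a change.** The best case for a change is that it costs only wording. Appendix C records that the regulator asked the sponsor to show that the primary analysis suits the chosen estimand, and the current text contains no such argument. Section 9.2 assigns a set to every other class of analysis but not to the imputation. The planned tabulations (withdrawal reasons, discontinuations by dose level) are descriptive and cannot identify would-be non-tolerators on placebo. All of this is accurate.

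It does not lead to a better analysis. Imputing over all treated subjects answers a question about a wider population and leaves the tolerator mismatch where it was. Writing in a bridging assumption is also less simple than it looks. The obvious one, that would-be non-tolerators score like tolerators on placebo given the pre-dose score, is not necessary: the table shows zero bias with non-tolerators 1 SD lower when overlap is complete or both kinds of leaver differ equally. Nor is it sufficient. If non-tolerators match the tolerator mean but placebo-only leavers score 0.5 to 1 SD lower, the bias is −(1 − a/(s+a)) × b/(s+b) × g × 21.75. That is −0.6 to −1.1 points at 20%/10% and −0.9 to −1.7 at 15%/15%, both with half overlap. Such a sentence would put an incorrect claim into the protocol.

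On the imputation set, the purpose in Appendix C and the placing of the method directly after the count of subjects lost before Visit 5 both point to the ITT set. The detailed SAP is not in the text reviewed, so it cannot be said to omit the set.

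**Conclusion.** No change to the plan follows. The mITT contrast equals the stated effect only if placebo subjects with Visit 5 scores have the same mean placebo response as everyone who would tolerate 20 mg of active drug. Both would-be non-tolerators who stay on placebo and tolerators who would leave only on placebo bear on that. A reader of the results should keep it in mind, but tolerance of a drug not taken is unobservable, so no analysis set in this design would deliver the target directly. Accepting this is a fair trade-off for a fixed-dose parallel trial with blinded titration.

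The unnamed imputation set is a gap that analysts will fill sensibly. Only the ITT set serves the stated purpose, and an analyst who uses it will have to impute the Visit 5 pre-dose score as well, because early leavers cannot otherwise enter the model. The result describes all treated subjects, not tolerators.

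The likely size is about −1.9 to +3.6 points on a planned 18, and 6.4 in the one-sided extreme. These figures rest on assumed dropout splits, overlaps and shifts of 0.5 to 1 SD, 1:1 allocation, and counting every departure on active as intolerance. Section 3.6 lists other reasons for leaving, so that last assumption tends to overstate non-tolerance. Significance at the planned effect is robust.
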